#### 17.7 ECG

ECG interpretation (Normal / Abnormal, not clinically significant/ Abnormal, clinically significant) and ECG measurements (RQT, QTcF, QTcB, PR and QRS) will be tabulated/summarized by visit and ECG time point (Before IMP administration and End of IMP administration (+15 min)). The three 12-lead ECG performed at each visit/time point will be combined as one measurement using the average of the three results (for ECG measurements), and the worst outcome of the three results for ECG interpretation. If available, reason for ECG abnormality will be listed.

Categorical analysis of QT, QTcB and QTcF interval data based on the number of subjects meeting or exceeding predefined limits in terms of absolute QT, QTcB and QTcF intervals (>450 ms or >480 ms or >500 ms) or changes from baseline (change of >30 ms or >60 ms) will be presented at baseline and at any post-baseline visit.

Additionally, categorical analysis of PR interval data based on the number of subjects meeting or exceeding predefined limits in terms of absolute PR (>200 ms or >220 ms) or changes from baseline (change of >25%) will also be presented at baseline and at any post-baseline visit.

Lastly, categorical analysis of QRS interval data based on the number of subjects meeting or exceeding predefined limits in terms of absolute QRS (>110 ms or >120 ms) or changes from baseline (change of >25%) will also be presented at baseline and at any post-baseline visit.

A listing of these subjects will be produced.

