²² The day 8 visit can be omitted after approval by the sponsor medical monitor if there have been no AEs fulfilling the DLT criteria in the previous 6 cycles.
²³ To be completed as indicated to confirm response, new symptoms, end of treatment visit or at the physician discretion, see Section 9.2.
²⁴ Cytokine, complement and PK sampling to be taken at Cycles 1 and 2 Day 3 after infusion, see Table 1-3 and Table 1-4.
²⁵ A complete general physical examination will be done at the screening and Cycle 1 Day 1 visits. At subsequent visits and as clinically indicated limited symptom-directed physical examinations should be
performed.
26 Any AST, ALT, and/or bilirubin > grade 2 needs to be checked 2×/week for up to 4 weeks and until resolution or return to baseline.
27 Reneat at least once more, i.e. on Day 5 if AST, ALT, or bilinibin > grade 1 and > 1.5×baseline.
28 If no AST. ALT. and/or bilimbin > grade 2 elevations are observed in Cycle 1 and 2, the visit at Cycle 3 Day 3 can be omitted
²⁹ The PET must be combined with CT and the CT portion must be of similar diagnostic quality to CT alone. The PET-CT must be performed before any optional tumor biopsy to avoid potential false positive
findings. The baseline PET-CT assessment during screening should be performed at the closest date as possible from start of trial treatment, at least one week before tumor bionsy. Of note, if tumor leasons
showed no avidity at baseline, no further PET scans should be performed, but CT scans only.
³⁰ To be performed only if a patient, who has been exposed to GEN1029, did not have any PET-CT scans while on treatment and displayed avidity at screening.
³³ Dexamethasone 4 mg/p.o. one day before dosing at Cycles 1 and 2 and 10 mg, i.v. at Day 1 before dosing and at Day 2 in Cycles 1 and 2. If a drug-related > grade 2 elevation of ALT and/or AST is observed
during the second cycle or thereafter, Dexamethasone pre-medication should be continued/re-introduced. In this case, Dexamethasone can be given orally on the day after the dosing day (Section 6.4.1).

Treatment Cycle	Screening	Cycle 1-3		Cycle 4-PD	End of Treatment	Unscheduled	
Day	-	1d	2d	8d	1d	-	
Before Infusion (on infusion days)	1	3	3 ^a	3	3	1	1 ^b
End of infusion (+15 minutes)		3			3		
End of infusion + 2 hours (± 15 minutes)		3					
End of infusion + 4 hours (± 30 minutes)		3					

Table 1-2 ECG Assessments in Dose Escalation Part – Applicable for Both Regimens

1 - Single ECG assessment

3 - Triplicate ECG assessments

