25 Repeat at least once more, i.e. on Day 5 if AST, ALT, or bilirubin > grade 1 and > 1.5×baseline.
²⁷ Only required at Cycles 1 and 2
²⁸ All patients must have a sample taken at Day 1 and 8 of Cycle 1 and at Day 8 of Cycle 3. If the visit occurs on an infusion day, the sample must be taken before IMP treatment.
$\frac{30}{10}$ Dexamethasone 4 mg/p.o. one day before dosing at Cycles 1 and 2 and 10 mg. i.v. at Day 1 before dosing and orally at Day 2 in Cycles 1 and 2. If a drug-related \geq grade 2 elevation of ALT and/or AST is
observed during the second cycle or thereafter, Dexamethasone pre-medication should be continued/re-introduced. In this case, Dexamethasone can be given orally on the day after the dosing day (Section

6.4.1).

³¹ If no AST, ALT, and/or bilirubin \geq grade 2 elevations are observed in Cycle 1 and 2, the visit at Cycle 3 Day 3 can be omitted.

Table 1-7 ECG Assessments in Expansion Part – Applicable for Both Regimens

Treatment Cycle	Screening	Cycle 1-3		Cycle 4-PD	End of Treatment	Unscheduled
Day	-	1d	8d	1d	-	
Before Infusion (on infusion days)	1	3	3	3	1	1 ^a
End of infusion (+15 minutes)		3		3		

1 – Single ECG assessment 3 – Triplicate ECG assessments

^a Optional.

Table 1-8 PK Sampling in Expansion Part – Applicable for Both Regimens

Treatment Cycle	Screening	Cycle 1-3		Cycle 4-PD	Unscheduled
Day/Week	-	1d	8d	1d	
Before Infusion (on infusion days)	X	Х	Х	Х	X^1
End of infusion (+15 minutes)		Х		Х	

¹ Optional.

Table 1-9 Vital Signs during the Expansion Part – Applicable for Both Regimens

Pre-infusion (up to 30 min before infusion)
At the end of infusion $(\pm 10 \text{min})^*$
1 hour after end of infusion (\pm 10 min)
2 hours after end of infusion (\pm 15 min)

*If infusion lasts for more than 60 minutes, vital signs should be assessed every 30 minutes (± 5 minutes) for the remaining duration of infusion.

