11.4.2.3 Other Safety Data

ECG

12-lead ECGs including PR, QRS, QT, QTcF, and RR intervals will be obtained for each patient during the trial in accordance with Table 1-2 (dose escalation part) and Table 1-7 (expansion part). ECG data will be read and interpreted centrally.

Categorical analysis of QT/QTc interval data based on the number of patients meeting or exceeding predefined limits in terms of absolute QT/QTc intervals or changes from baseline will be presented. In addition, a listing of these patients will be produced.

Vital signs

Data on vital signs will be tabulated and listed; notable values will be flagged.

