## 3. Trial Design and Objectives

The present SAP covers the escalation part only as the expansion part of the trial was not initiated.

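### The SAP's ECG summary by time point leaves out, without a stated reason, the +2 h and +4 h triplicates collected on Day 1 of Cycles 1-3 in dose escalation

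*SAP*

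**What the plan says.** SAP 17.7 tabulates ECG interpretation and ECG intervals by visit and ECG time point. The time points are given in a parenthesis: "Before IMP administration and End of IMP administration (+15 min". The three tracings at a time point are averaged for the intervals, and the worst of the three is taken for the interpretation. The output is Table 14.03.41.01.

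The scope is stated in SAP section 3: "The present SAP covers the escalation part only as the expansion part of the trial was not initiated".

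The protocol schedule for that part is "Table 1-2 ECG Assessments in Dose Escalation Part – Applicable for Both Regimens". Besides the pre-infusion and end-of-infusion rows, it has two further triplicate rows on Day 1 of Cycles 1-3: "End of infusion + 2 hours (± 15 minutes") and "End of infusion + 4 hours (± 30 minutes"). The protocol's statistics section (11.4.2.3) ties the escalation ECGs to this schedule: they "will be obtained for each patient during the trial in accordance with Table 1-2".

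SAP 17.7 also plans categorical analyses of QT, QTcB, QTcF, PR and QRS at baseline and post-baseline, with no restriction to particular time points, and a listing of the subjects concerned. Listing 16.02.03.11 covers ECG results. SAP section 5, which records departures from the protocol, mentions the dose-determining set, the PK analysis set and the unused expansion part, but nothing about ECG time points.

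**The concern.** The SAP's list of time points is shorter than the schedule under which the data were collected. The parenthesis in 17.7 does not read as an example. It reads as the definition of the rows to be programmed, so two scheduled post-infusion time points would drop out of the only planned table of ECG means over time.

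This matters because the trial is first-in-human and establishing the safety profile is a primary objective. Protocol Table 1-3 takes PK samples at the same four Day 1 time points (pre-infusion, end of infusion, +2 h, +4 h) with the same windows after infusion, so these ECGs have matched drug concentrations. The categorical analyses detect large individual changes. A modest average shift is what a table of means by time point is meant to show, and for the 2-4 h window there would be no such table.

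**Working it through.** The plan gives no figure to reproduce, so the check is a comparison of schedules and a count.

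**Inputs.** Protocol Table 1-2 (escalation), protocol Table 1-7 (expansion) and SAP 17.7. Entries are triplicate sets on infusion day (Day 1).

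| Day 1 time point | Table 1-2, Cycles 1-3 | Table 1-2, Cycle 4 to PD | Table 1-7 (expansion) | Named in SAP 17.7 |
|---|---|---|---|---|
| Before infusion | yes | yes | yes | yes |
| End of infusion (+15 min) | yes | yes | yes | yes |
| End of infusion +2 h | yes | no | no | **no** |
| End of infusion +4 h | yes | no | no | **no** |

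Table 1-2 also has one triplicate on Day 2 (24 h ± 2 h after the end of the Day 1 infusion) and one on Day 8 in each of Cycles 1-3. Both sit in its before-infusion row, although neither is an infusion day in either current regimen.

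**Count per patient, Cycles 1-3.**

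- Sets scheduled per cycle: 4 (Day 1) + 1 (Day 2) + 1 (Day 8) = 6.
- Sets scheduled over three cycles: 6 × 3 = 18.
- Sets left out per cycle: 2 (+2 h and +4 h).
- Sets left out over three cycles: 2 × 3 = 6, which is 6 × 3 = 18 individual tracings.
- Share of all scheduled sets: 6 / 18 = 33%.
- Share of Day 1 sets only: 6 / (4 × 3) = 6 / 12 = 50%.
- From Cycle 4 onward: 0 left out, because Table 1-2 itself has only the two named time points.

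The count assumes three completed cycles. A patient who stops after Cycle 1 has 2 of 6 sets left out, which is the same 33%.

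**Where the +2 h and +4 h values can still appear.**

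- *Table of means by visit and time point (14.03.41.01):* not under the wording of 17.7.
- *Categorical analyses:* no time-point limit is written, so they can enter. The cut-offs are absolute QT/QTc above 450, 480 or 500 ms or a change above 30 or 60 ms; PR above 200 or 220 ms or a change above 25%; QRS above 110 or 120 ms or a change above 25%.
- *ECG listing (16.02.03.11):* individual values can be listed.

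**What remains uncovered.** Take a QTcF rise of 30 ms or less in subjects who stay at or below 450 ms, present at 2-4 h and gone by 24 h. It crosses no categorical cut-off and is absent from the pre-infusion, end-of-infusion, Day 2 and Day 8 summaries. It would be visible only to someone reading the listing line by line. The same holds for a PR or QRS change of 25% or less that stays below the absolute limits.

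**The case against.** The strongest reply is that nothing the protocol promised is lost. Protocol 11.4.2.3 promises a categorical QT/QTc analysis and a listing of the patients concerned. SAP 17.7 delivers both and adds PR and QRS. The table of means is extra, ECG is not a listed endpoint, and MTD determination rests on DLTs. SAP 4.8 also says in general terms that available data go into listings and tabulations. All of this stands, and it keeps the point small. It does not answer the mismatch: once the SAP plans a summary by time point, a specific list of time points in 17.7 is what will be programmed, and the general sentence in 4.8 does not override it.

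A reader might infer three stronger things that the documents do not support.

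- *That a delayed ECG effect would be invisible outside the outlier counts.* The 24 h and Day 8 triplicates are separate visits, so the by-visit summary plausibly covers them. An effect lasting that long should show there.
- *That the SAP applied a schedule foreign to this part of the trial.* The two named time points are indeed the only rows of "Table 1-7 ECG Assessments in Expansion Part – Applicable for Both Regimens", and text left over from the expansion part is a possible explanation. But both are also rows of the escalation table, and together they make up its complete Day 1 schedule from Cycle 4 onward. The documents do not say where the wording came from.
- *That half of the ECG data is dropped.* The 50% figure applies to Day 1 of Cycles 1-3 only. Against all sets scheduled in Cycles 1-3 it is one third, and the values remain available for the categorical counts and the listing.

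**Conclusion.** The point holds in a limited form. As written, SAP 17.7 excludes the +2 h and +4 h triplicates from Table 14.03.41.01 although the escalation schedule collects them, and no reason is recorded. The size is 2 of 4 Day 1 time points in Cycles 1-3, or 6 of 18 scheduled triplicate sets for a patient completing three cycles. The consequence is confined to a transient mean shift at about 2-4 h that stays below the categorical cut-offs.

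This rests on two assumptions: that the parenthesis in 17.7 is followed literally, and that the absence of a time-point limit in the categorical analyses means that all post-baseline time points count. If the second is wrong and the categorical analyses are built from the two named time points only, the gap is wider, which is why the fix asks for that to be stated. Neither the MTD nor any listed endpoint is affected. This is a free improvement.

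**What to change.** In SAP 17.7:

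1. Add end of infusion +2 h and +4 h (Day 1, Cycles 1-3) to the named time points, so that Table 14.03.41.01 shows all four Day 1 time points in those cycles and two from Cycle 4 onward.
2. Label the Day 2 (24 h) and Day 8 triplicates as separate visits, so that they do not appear under a pre-infusion label.
3. State that the QT, QTcB, QTcF, PR and QRS categorical analyses use every post-baseline time point.

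If the two time points are left out on purpose, record that and the reason in SAP section 5. The ECGs are already scheduled by the protocol, so the cost is one sentence in the SAP and extra rows in one table, with no new data collection.

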## 18. Other Safety Data

## 18.1 Immunogenicity (anti-drug antibodies) of GEN1029

Data on immunogenicity (anti-drug antibodies) of GEN1029 will be summarized as described below on the immunogenicity set.

Titers of GEN1029 will be listed additionally to their presentation in graphs of PK concentration and pharmacokinetic table

[figure not shown]
Positive/negative host immune response to GEN1029 will be tabulated by visit. For post-baseline results, a subject will have a positive ADA status if negative at baseline and at least one positive post-baseline result, or positive at baseline and at least one positive post-baseline result with a titer higher than baseline. Of note, subjects with no post-baseline ADA assessment will have a missing ADA status.

Of note, ADA positivity requires confirmation in 2 assay steps. First step has many false positive; the second assay step (confirmation) ensures specificity of the assay. Only confirmed ADA positivity results will be considered as positive.

Page 29 of 44

TPL N°: eTPL SA-02-01 Of SOP SA-02.08 TPL Effective Date: 31 Mar 2016

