Demographics, disease status	Х												
Prior cancer therapy/surgery	Х												
Medical History	Х												
Height	Х												
Body Weight ⁶	Х	Х				Х		Х					
Physical Examination ²⁵	Х	Х				Х		Х					
Vital Signs ⁷	Х	Х	Х		Х	Х	Х	Х					X ¹⁴
Liver ultrasound	Х												
ECG						Plea	ise see Tal	ble 1-2 for detail	s of ECG asse	ssments			
PET-CT scan ²⁹	X ²⁹			X^8			X ⁸					X ³⁰	
Efficacy assessment (CT-Scan)				X ⁹			X ⁹	X ²³					X ¹⁴
ECOG status	Х	Х				Х		Х					X^{14}
Adverse Events ⁵	Х	Х	Х	Х	Х	Х	Х	Х	Х	Х	X ¹⁸		X^{14}
Concomitant Medication	Х	Х	Х	Х	Х	Х	Х	Х	X ¹⁹	X ¹⁹	X ¹⁹		X ¹⁴
Pre-medication ³³		Х	Х										
IMP administration		Х				Х							
End of trial												X ²⁰	
Laboratory assessments ¹⁰													I.
Hematology	Х	Х	Х		Х	Х	Х	Х	Х	Х			X ¹⁴
Biochemistry ²⁶	Х	Х	Х	X ²⁷	Х	Х	Х	Х	Х	Х			X^{14}
Urinalysis	Х	Х				Х		Х	Х	Х			X^{14}
							1		1	1			
Pregnancy Test ¹¹	X	X				X		X					X ¹⁴
ADA (Immunogenicity)	X	Х				X		X	X	X			X ¹⁴
Hepatitis B, C, CMV ¹²	Х			I		L			1 CDV	1.			X ¹⁴
PK Sampling	v 13	1	 	1	1	P.	lease see	1 able 1-3 for deta	alls of PK sam	ipiing	1		V 14
Tumor blopsy	Λ	V 15	+		V 15		V 17	A ^{···}					X ¹⁴
Immunophenotyping		Χ	1		D1		X''	Λ		lamont cor1			Λ
Cytokine and circulating factors		_			riea	se see 1	iule 1-4 IC	or details of cytol	cine and comp	iement sampli	ing		

Table 1-1 Visit evaluation schedule Dose Escalation Part – Biweekly Regimen (Q2W) and Priming Regimen (Priming/Q2W)

Footnotes to Trial Flowchart: Dose Escalation Part - Biweekly Regimen (Q2W) and Priming Regimen (Priming/Q2W)
¹ The duration of one cycle is 14 days. Treatment can continue until PD.
² If the patient shows PD, starts a new anti-cancer treatment or withdraws from treatment due to another reason, the end of treatment visit should be performed as soon as possible after decision of
discontinuation.
³ The specified visit windows are in accordance with the previous visit. However, within 28 days from treatment start (corresponding to the DLT period), max. 2 doses of GEN1029 in the O2W regimen and
in the priming regimen can be administered. At Cycles 2 and 3, Day 1 of the next cycle should be performed 7 days ± 1 day after Day 8 of the previous cycle and from Cycle 4 and onwards, Day 1 of the
next cycle should be performed 7 days ± 3 days after Day 8 of the previous cycle.
⁴ Informed consent must be obtained before or at Screening prior to making any screening assessments.
⁵ Adverse Events should be reported from the time the informed consent is signed.

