9.6.2 Analytical Procedures

The detection and characterization of antibodies to GEN1029 will be performed using a validated assay methods under the supervision of the sponsor. All samples collected for detection of antibodies to GEN1029.

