9.6.3 Immunogenicity Assessments

Antibodies to GEN1029 will be evaluated in plasma samples collected from all patients according to the visit schedule. These samples will be tested by the sponsor or sponsor's designee.

Plasma samples will be screened for antibodies binding to GEN1029 and the titer of confirmed positive samples will be reported. Two titer methods will be used; one method will determine the response against Hx-DR5-01 and the other against Hx-DR5-05. Other analyses may be performed to verify the stability of antibodies to GEN1029 and/or further characterize the immunogenicity of GEN1029.

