## 4.6 Calculated Variables

• Baseline is defined as the available data from the latest recorded measurement made before the first IMP administration (trial day 1). Measurements done on the same date as the first IMP administration will be considered as done before the first IMP administration unless specified otherwise (i.e the time associated with the date implies that the measurement was done after the first IMP, even if it is during the same day). For PK variables, the IMP administration on Day 1 of each cycle will be time 0.

Page 11 of 44

TPL N°: eTPL SA-02-01

TPL Version: 02

Of SOP SA-02.08
TPL Effective Date: 31 Mar 2016
Approved in Vault: 07 Mar 2022

- Change from baseline is defined as the post-baseline value baseline value.
   Change from baseline will be missing when either post-baseline or baseline value is missing.
- For laboratory data, local change from baseline will be calculated as the post-baseline local value local baseline value. Local change from baseline will be missing when either local post-baseline or local baseline value is missing.
- For laboratory data, central change from baseline will be calculated as the post-baseline central value central baseline value. Central change from baseline will be missing when either central post-baseline or central baseline value is missing.
- Percent change from baseline is defined as 100\*(post-baseline value baseline value)/baseline value. If the baseline value is 0 and the post-baseline value is 0, the change from baseline and the percent change from baseline are both 0. If the baseline value is 0 and the post-baseline value is not 0, the percent change from baseline will be undefined (missing value).
- Time (in months) from first diagnosis of primary site to start date of IMP: (start date of IMP date of first diagnosis)/30.4375.
- Time (in months) since most recent recurrence/relapse or progression to start date of IMP: (start date of IMP date of most recent recurrence/relapse or progression)/30.4375.
- Time (in months) since last biopsy: (start date of IMP date of most recent biopsy)/30.4375.
- Total number of days in trial: max (last contact date, date of death) start date of IMP + 1.
- Total treatment duration (days): (end date of IMP start date IMP) +1,
   End date of IMP related to

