In addition, time to onset of first AESI event (for subjects with at least one event), total number of AESI events, total number and percentage of AESI events with outcome of resolution, and time to resolution of each AESI event (for events which are resolved) will be summarized by AESI category using descriptive statistics. AESI events with partial start date will be imputed accordingly to the rules described in section 4.7. The same outputs will be created for the other event of interest: Pyrexia.

Time to onset of first AESI event will also be presented graphically by AESI category using Kaplan-Meier curves (one plot for each AESI category); in these Kaplan-Meier curves, subjects with no AESI will be censored at the end of the treatment period. Time to onset of first other event of interest: Pyrexia, using Kaplan-Meier curves will also be displayed.

AESI will also be presented graphically using swim lane plots. Plots will be performed individually for each subject, by dose level, and will show the reported AESI by category on a time-based x-axis (arrow will be used to show ongoing AEs). Plots will also include lines to show start date in the study (i.e., informed consent date) and last contact date of subject, as well as start and end dates of on-treatment period. Other event of interest: Pyrexia, will also be displayed on those swim lane plots.

Listings of all adverse events (including those from the pre and post-treatment periods) will be provided including the screening number/patient number (including site and country), age, race, sex, regimen, dose level, tumor type, verbatim, PT, SOC, duration of the event, highest severity, action taken, outcome, causality, date of onset, cycle of onset, date of resolution, days since the first dose, days since the latest dose, serious (Y/N), DLT (Y/N), infusion reaction (Y/N) and the treatment-emergent flag. AEs collected during the pre-treatment and post-treatment period will be flagged. Similar listings will also be created for each adverse events of interest separately.

Adverse Event will also be presented in a table by ADA status as applicable.

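### SAP 18.1 lets any single post-dose titer above one baseline titer make a baseline-positive subject ADA positive, so assay noise alone can decide the label

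*SAP*

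**What the plan says.** For a subject with ADA before treatment, SAP 18.1 requires the subject to be "positive at baseline and at least one positive post-baseline result with a titer higher than baseline". One sample is enough and any rise counts. The section then describes a two-step assay and says "Only confirmed ADA positivity results will be considered as positive"; this concerns whether a sample is positive.

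The reference value comes from SAP 4.6: "Baseline is defined as the available data from the latest recorded measurement made before the first IMP administration". It is a single value, although protocol Table 1-1 schedules ADA samples at both screening and Cycle 1 Day 1. After the first dose, Table 1-1 schedules ADA on Day 1 of every later cycle, at end of treatment, and 30 and 70 days after last dosing.

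Protocol 9.6.3 states "Two titer methods will be used; one method will determine the response against Hx-DR5-01 and the other against Hx-DR5-05". SAP 18.1 refers only to a titer and does not say which method decides or how the two combine. Protocol 9.6.2 says the assay methods are validated, but neither document gives the precision, the dilution step or a minimum meaningful ratio. None appears in SAP 4.4 or protocol 11.4.4 either.

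The ADA grouping is used in several outputs. SAP 17.3 says "Adverse Event will also be presented in a table by ADA status as applicable". SAP 17.4 splits fatal AEs, SAEs and grade 3 or higher AEs by ADA positivity, SAP 17.2 presents treatment duration by ADA status, and Tables 14.02.06.01 and 14.02.06.02 split the PK parameters.

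**The concern.** The rule compares the largest of several noisy readings with one noisy reading. A subject whose antibodies never changed will sometimes exceed baseline by chance, and each further sample is another opportunity. Two consequences follow.

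- Among baseline-positive subjects, the split between positive and not positive is partly random. Those who do not cross the line have no category of their own, so tables by ADA status cannot separate them from subjects who never had ADA. Protocol 2.1.2 reports that liver toxicity with an earlier multivalent anti-DR5 compound correlated with pre-existing ADA, and transaminase elevation is an AE of special interest here. This is therefore a group worth seeing clearly.
- The chance of a false label rises with time on treatment, because more samples are taken. SAP 17.2 presents treatment duration by ADA status, so the rule itself can create an association between the two.

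**Working it through.** The plan states no misclassification rate, so there is no figure to reproduce. The check asks how often an unchanged baseline-positive subject would be labelled positive.

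**Number of post-dose samples (k).** From Table 1-1, a subject who starts c cycles and completes follow-up has c − 1 later Day 1 samples plus three (end of treatment, 30 days, 70 days), so k = c + 2. That gives k = 3 after one cycle, 5 after three and 8 after six. It is smaller if the subject withdraws or dies.

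**Assumptions (not in the documents).** Assay SD of 0.25 to 1.0 log2 units; 2-, 3- or 4-fold dilution steps; independent errors; no true change.

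**Tie-free titer.** Baseline and the k later readings are exchangeable, so P(at least one exceeds baseline) = k/(k + 1): 1/2 = 50%, 3/4 = 75%, 5/6 = 83%. This is an upper reference, because titers read in steps produce ties and a tie is not a rise.

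**Stepped titer, k = 1, by formula.** With the true titer spread evenly within a step and D the difference of two readings in step units, P(tie) = E[max(0, 1 − |D|)] and P(rise) = (1 − P(tie))/2.

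- SD 0.25, 4-fold steps (2 log2 units): SD of D = 0.25 × √2 / 2 = 0.177. E|D| = 0.177 × 0.798 = 0.141. P(rise) ≈ 0.141/2 = 7%.
- SD 1.0, 2-fold steps: SD of D = 1.414. P(|D| < 1) = 0.521. E[|D|; |D| < 1] = 1.128 × (1 − e^(−0.25)) = 0.250. P(tie) = 0.521 − 0.250 = 0.271. P(rise) = 0.729/2 = 36%.

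**Stepped titer, any k.** Simulation of 200,000 subjects, one titer, strict inequality:

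| Dilution step | SD (log2) | k = 1 | k = 3 | k = 5 |
|---|---|---|---|---|
| 2-fold | 0.25 | 14% | 26% | 32% |
| 2-fold | 0.5 | 26% | 45% | 55% |
| 2-fold | 1.0 | 36% | 60% | 70% |
| 3-fold | 0.25 | 9% | 16% | 20% |
| 3-fold | 0.5 | 18% | 32% | 39% |
| 3-fold | 1.0 | 30% | 51% | 61% |
| 4-fold | 0.25 | 7% | 13% | 16% |
| 4-fold | 0.5 | 14% | 26% | 32% |
| 4-fold | 1.0 | 26% | 46% | 55% |

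**Sensitivity (2-fold steps).**

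- A rise in either of two titers with independent errors counts: 45%, 70% and 84% at k = 3, and 53%, 79% and 91% at k = 5, for SD 0.25, 0.5 and 1.0.
- Drug interference lowers post-dose titers by one step: 6% and 9% (k = 3 and 5) at SD 0.5; 30% and 39% at SD 1.0.

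**Effect of a minimum ratio (2-fold steps, one titer).** A 4-fold rise over a single baseline, k = 3 to 5, leaves about 0.1% at SD 0.25, 6-9% at SD 0.5 and 30-39% at SD 1.0. A 4-fold rise over the higher of two pre-dose titers, k = 3, leaves 1.5%, 7.3% and 14.4% at SD 0.5, 0.75 and 1.0. If either of two independent methods may trigger, the last range becomes 1 − (1 − 0.015)² = 3% to 1 − (1 − 0.144)² = 27%.

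**The case against.** The best case for leaving the text alone has four parts.

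- **These subjects do carry ADA.** They have confirmed antibodies before and after dosing, and protocol 11.4.4 plans the association by positive versus non-positive ADA, not by a rise. Counting them as positive is not contamination on that reading. This stands as far as it goes, but SAP 18.1 does not count all carriers as positive. It divides them by a titer comparison, and that division is what noise disturbs.
- **Steps already impose a minimum.** With stepped titers the smallest countable rise is one dilution step, and if the step is 4-fold, a 4-fold floor adds nothing. This is correct, and it is why the remedy should be tied to the assay rather than to a fixed multiple.
- **Reach is small.** SAP 4.4 conditions subgroup analyses on at least 5 subjects per subgroup per dose level. About 44 to 46 biweekly subjects (SAP 3.3 and 4.5 differ on the Intensified count) over six dose levels average 7 to 8 per level, too few for two groups of 5 at most levels. The outputs are descriptive, and the MTD rests on DLTs. This stands and limits the consequences.
- **The data stay visible.** Titers are listed and shown with the PK concentration graphs. That allows a reader to check individual subjects, but it does not correct tables already split by status.

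A reader might infer that about half or more of unchanged subjects would be mislabelled, or that a rise in either titer is enough. The documents support neither. The first is exact only for a titer without ties, and assay precision and dilution step are not given. The second is one possible reading of text that does not say which titer decides.

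**Conclusion.** The concern holds as a weakness in a stated rule, not merely as missing detail: applied exactly as written, SAP 18.1 will label some unchanged baseline-positive subjects ADA positive through assay noise, and more of them the longer they are sampled. For one titer the share is about 7-36% with one post-dose sample and 13-70% with three to five. This rests on the assumed SDs and dilution steps, independent errors and no true change. Drug interference would lower it; a rule that either titer may trigger would raise it.

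Only baseline-positive subjects are affected, and the documents do not say how many there are. As an illustration, if 10-20% of the 48 subjects were positive at baseline (5 to 10), the one-titer range at k = 3 (13-60%) would mislabel between 5 × 0.13 ≈ 1 and 10 × 0.60 = 6, if none truly changed. That is few in absolute terms, but it can matter in tables by dose level. The dose-finding conclusion is untouched.

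**What to change.** In SAP 18.1:

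1. Count a baseline-positive subject as ADA positive only if a post-baseline titer exceeds the pre-dose titer in the same component method by at least the minimum ratio derived from that assay's validated titer variability, and by more than one dilution step. Use 4-fold only as a default where dilutions are 2-fold.
2. For this comparison, take the higher of the screening and Cycle 1 Day 1 titers as the pre-dose value, and note it as an exception to the general baseline in SAP 4.6.
3. State how the Hx-DR5-01 and Hx-DR5-05 results combine into one subject status.
4. Tabulate baseline-positive subjects without such a rise as a separate category.

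The cost is a few sentences of SAP text and a revised derivation. No new samples are needed, since both pre-dose samples are already scheduled. The validated ratio has to come from the assay reports. The downside is that true rises below the threshold are not counted, and with an imprecise assay some false labels would remain.
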